3.2 Study Endpoints

- All-cause mortality.
- Ordinal Scale of Clinical Improvement, absolute values and changes from start of treatment to Days 2, 3, 7, 15, and 30.
- Time to a 1-point decrease on the Ordinal Scale of Clinical Improvement from start of treatment.

- Area under the severity versus time curve, where severity is defined by the Ordinal Scale of Clinical Improvement and time is measured from start of treatment to Days 2, 3, 7, 15, and 30.
- Days of supplemental oxygen or mechanical ventilation from start of treatment (up to 90 days).
- First Intensive Care Unit (ICU) discharge
- Days in ICU from start of treatment (up to 90 days).
- Discharge from hospital.
- Days hospitalized from start of treatment (up to 90 days).
- Severity of ARDS as defined by the Berlin criteria, absolute values and changes from start of treatment to Days 2, 3, 7, 15, and 30.
- Cytokine and biomarker results, absolute values and changes from start of treatment to Days 2, 3, 7, 15, and 30.
- Adverse events (AEs) and serious adverse events (SAEs) within 90 days from start of treatment.

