7.2 Final Analysis

The final tables, listings, graphs, and data analyses will be conducted once all study participants have completed the study (through the Day 90 visit) and the clinical database has been locked.

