11.6 Intensive Care Unit (ICU) Discharges

The time until discharge from ICU will be compared between groups with observation time up to 90 days. The total time from first administration of study drug will be taken from Study Drug Administration eCRF (dataset EX, First IP administration date). The date/time that subjects were admitted and discharged from ICU (from last hospitalization) will be taken from the Hospitalization eCRF page (dataset: AEHO).

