11.7 Days in ICU and Time to Discharge

Duration in the ICU (days) will be defined in two ways:

- (1) The interval from the subject’s date/time of ICU admission to the date/time the subject is discharged from the ICU (Hospitalization dataset: AEHO). If a subject is admitted to the ICU multiple times, then all ICU visits will be added together to calculate the duration in ICU.
- (2) The interval from the subject’s date/time of ICU admission after study drug administration to the date/time the subject is discharged from the ICU (Hospitalization dataset: AEHO). If a subject was admitted to the ICU multiple times, then all ICU visits will be added together to calculate the duration in ICU.

Those subjects that were not admitted to the ICU or have no documentation of being discharged from the ICU will be censored for time to event analysis and will be imputed as the highest or lowest score for purposes of continuous outcome analysis.

The following censoring/ imputation rules will be followed:

- (1) If subjects do not have a documented admittance into the ICU, the duration in ICU will be censored at Day 1, or an imputed score of zero.
- (2) If subjects are in ICU through the entire follow-up phase, then the duration in ICU will be censored at the end of study date (maximum of 90 days), or imputed as the days in the study.
- (3) If subjects die while in ICU, then the duration in ICU will be censored at the date of death, or imputed as the days until death.
- (4) If subjects withdraw from study (any reason) while in the ICU, then duration in ICU will be censored at the date of study withdrawal or imputed as the number of days until withdrawal.
- (5) If subjects are in ICU at the time of database lock and analysis (unlikely, but possible), the duration in ICU will be censored on the date of database lock or imputed as the number of days until database lock.

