11.9 Duration of Hospitalization

Duration of hospitalization (days) will be defined in two ways:

- (1) The interval from the subject's date/time of hospital admission to the date/time the subject is discharged from the hospital (Hospitalization dataset: AEHO). If a subject is

hospitalized multiple times, then all hospitalizations will be added together to calculate the duration of hospitalization.

(2) The interval from the subject's date/time of hospital admission after study drug administration to the date/time the subject is discharged from hospital (Hospitalization dataset: AEHO). If a subject is hospitalized multiple times, then all hospitalizations will be added together to calculate the duration of hospitalization.

Those subjects that were not admitted to hospital or have no documentation of being discharged from the hospital will be censored for time to event analysis and will be imputed as the highest or lowest score for purposes of continuous analysis.

The same censoring/imputation rules as outlined above for ICU will be followed:

- (1) If subjects do not have a documented admittance into the hospital, the duration of hospitalization will be censored at Day 1.
- (2) If subjects are in the hospital through the entire follow-up phase, then the duration of hospitalization will be censored at the end of study date (maximum of 90 days).
- (3) If subjects die while in the hospital, then the duration of hospitalization will be censored at the date of death.
- (4) If subjects withdraw from study (any reason) while in the hospital, then duration of hospitalization will be censored at the date of study withdrawal.
- (5) If subjects are in hospital at the time of database lock and analysis (unlikely, but possible), the duration of hospitalization will be censored on the date of database lock.

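### Rule (5) in SAP 11.7 and 11.9 runs an open ICU or hospital stay to database lock, although the endpoints and rule (2) stop at 90 days; the effect is rare and confined to the imputed durations

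*SAP*

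**What the plan says.** SAP 3.2 lists the two duration endpoints as "Days in ICU from start of treatment (up to 90 days") and "Days hospitalized from start of treatment (up to 90 days"). For ICU discharge, SAP 11.6 adds: "The time until discharge from ICU will be compared between groups with observation time up to 90 days".

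SAP 11.7 then gives five censoring and imputation rules. Two matter here:

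- Rule (2), for a subject in ICU through the whole follow-up phase: "the duration in ICU will be censored at the end of study date (maximum of 90 days), or imputed as the days in the study".
- Rule (5), for a subject in ICU when the database is locked: "the duration in ICU will be censored on the date of database lock or imputed as the number of days until database lock". It carries no 90-day limit.

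SAP 11.9 introduces its hospital list with "The same censoring/imputation rules as outlined above for ICU will be followed". Its own rule (5) says only that "the duration of hospitalization will be censored on the date of database lock", so the imputed value for hospital days comes from 11.7 by reference.

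On timing, SAP 7.2 schedules the final analysis "once all study participants have completed the study (through the Day 90 visit) and the clinical database has been locked". SAP 7.1 rules out an interim efficacy analysis. Its heading mentions 30-day outcomes, but its text describes no earlier lock.

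**The concern.** A subject who is in ICU from infusion through follow-up and is still there at lock satisfies rules (2) and (5) together. One gives at most 90 days and the other gives the days to lock. The SAP states no precedence, so two programmers could both follow it and produce different data sets.

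A subject whose stay began after infusion and is still open at lock does not literally meet rule (2), and falls under the uncapped rule alone.

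Lock is a single calendar date, so the rule (5) value grows with how early the subject enrolled. Two subjects with the same course over 90 days could receive different scores. At stake are the means, standard deviations and any continuous comparison of ICU and hospital days, in arms of about 30.

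**Working it through.** The plan gives no figure to reproduce: no variance, effect size or expected duration is stated for these endpoints. The check is a comparison of rules followed by simple arithmetic.

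**Inputs from the documents**
- Endpoint limit: 90 days from start of treatment (SAP 3.2).
- Arm size: about 30 (SAP 4).
- Study duration 6 months; participation at most 13 weeks (SAP 2).
- 1 month = 30.4375 days (SAP 8.6).
- Day 90 visit window: ± 7 days (Protocol 1.3).

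**Assumptions**
- The time from the last Day 90 visit to lock is not stated; 0 to 90 days is used.
- The origin for the days until lock is not stated; start of treatment is used, as in the endpoint.

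**Implied accrual period**
6 × 30.4375 − 13 × 7 = 182.6 − 91 = 91.6 days.

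**Value under rule (5)**
Last-enrolled subject: 90 + lag. First-enrolled subject: 90 + 91.6 + lag. Shift in the arm mean against a 90-day cap: (value − 90) / 30.

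| Lag to lock (days) | Last-enrolled (days) | First-enrolled (days) | Shift in arm mean, last-enrolled | Shift in arm mean, first-enrolled |
|---|---|---|---|---|
| 0 | 90 | 181.6 | 0.0 | 3.1 |
| 30 | 120 | 211.6 | 1.0 | 4.1 |
| 60 | 150 | 241.6 | 2.0 | 5.1 |
| 90 | 180 | 271.6 | 3.0 | 6.1 |

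At any lag, the difference of about 92 days between the two subjects comes from enrolment date alone.

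**Illustration of one arm**
Take one subject at 180 instead of 90 days: (180 − 90) / 30 = 3.0 days on the mean. Suppose the other 29 have mean 8 and SD 15 days (both assumed).
- With 90: mean = (29 × 8 + 90) / 30 = 10.7, SD 21.0.
- With 180: mean = (29 × 8 + 180) / 30 = 13.7, SD 34.7.

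**Time-to-event analyses**
The log-rank statistic and the Cox partial likelihood use the risk sets at event times only. Moving a censoring time from Day 90 to a later date changes no risk set at or before Day 90. If no later events are counted, nothing changes. In a simulated set of 60 subjects, two subjects censored at Day 90 (one per arm) were moved to 182 and 120 days. The log-rank z stayed at 0.558. The arm means of the same durations moved from 25.0 to 28.1 and from 21.7 to 22.7 days.

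**The case against.** The best defence is that the rule will almost never be used. The SAP itself calls the situation improbable. Scheduled follow-up ends at the Day 90 visit, and Protocol 8.3.4 does not oblige investigators to seek adverse events afterwards, so no planned visit would establish that a subject is in ICU at lock. This stands, and it is why the point is minor.

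The second defence is that rule (5) may be meant for an early lock. Protocol 10.1.2 lets the study be terminated at any time, and lock could then precede a subject's Day 90, giving a value below 90 days and no conflict. The SAP does not state this purpose, and its 7.2 describes the opposite order. The use is legitimate, though, and argues for capping the rule rather than deleting it.

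A trivial exception also exists: a last subject seen early in the ± 7-day window, followed by immediate lock, could fall within 90 days.

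A reader might infer more than the documents support:
- **That the main comparison is distorted.** SAP 11 makes Cox regression, with Kaplan-Meier and log-rank, the default primary analysis. It is essentially untouched if discharges after Day 90 are not counted.
- **That one subject would dominate an arm.** This can be true of a mean and SD under an assumed extreme value. SAP 9 also reports medians, and 11.7 and 11.9 name no test for the continuous analysis.
- **That readmissions after Day 90 would routinely enter.** Protocol 8.2.8 collects later admissions, but no contact is planned after Day 90 through which they would be found.
- **That longer follow-up is intended.** SAP 11.1 asks for the longest possible cut-off for survival only.

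**Conclusion.** Wrong as written, at low priority. Rule (5) conflicts with the 90-day endpoints and with rule (2), and makes the recorded duration depend on enrolment date for any subject it reaches. For hospital days, the censoring half is explicit in SAP 11.9 and the imputation half rests on the cross-reference to 11.7.

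The exposure is limited to the imputed continuous durations and their summaries: about 3 to 6 days on a 30-subject arm mean for one first-enrolled subject, given the stated 6-month and 13-week durations and an assumed lag to lock of 0 to 90 days. For a last-enrolled subject it is 0 to 3 days. If no subject is in ICU or hospital at lock, the effect is nil. The documents show no direction of bias between arms.

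**What to change.** In SAP 11.7 and 11.9, end rule (5) at the earlier of Day 90 from infusion and database lock, and write this out for both censoring and imputation in each section. Add one sentence stating that ICU days, hospital days and discharges after Day 90 are not counted. That sentence is needed most for hospital discharge, where the SAP has no counterpart to the 90-day observation limit in 11.6.

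Capping is preferable to deletion. It keeps a rule for a stay open at an early lock, and it covers a stay that began after infusion, which rule (2) does not literally reach.

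The cost is a few words in the SAP, with no new data and no design change. It should be made before unblinding, so that the choice between the two rules is not left until results are known.

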11.8 Days in Hospital and Time to Discharge

The number of subjects that were hospitalized and ultimately discharged from the hospital within 30 days from start of treatment will be summarized by number and percentage. Additionally, the two-sided exact 95% confidence intervals will be computed for each treatment's binomial proportion of hospital discharge. The hospital discharge rate will be compared between the treatments groups using Fishers Exact Test.

The total time (days) from first administration of study drug will be taken from Study Drug Administration eCRF (dataset EX, First IP administration date). The date/time subjects were discharged from the hospital will be taken from the Hospitalization eCRF page (dataset: AEHO).

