-  Monitoring for infiltration or extravasation at the site of peripheral venous access every 15 minutes from pre-infusion through 2 hours post-infusion.
-  As noted in footnote 3, adverse events will be monitored on a daily basis while the subject is hospitalized on study. For any allergic reaction, a tryptase blood sample will be collected and analyzed locally per protocol.
-  Outcome data includes information related to clinical status and survival including, but not limited to ARDS diagnosis by Berlin criteria, ICU information, hospitalization, disposition, and mortality.

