### **8.2.8 Hospitalization**

Information pertaining to the index hospitalization and any subsequent hospital admission will be collected including date of hospitalization, date of hospital discharge, reason for hospitalization, and disposition at time of discharge.

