### **8.2.9 Intensive Care Unit**

Information pertaining to the ICU admission and life-saving measures taken will be collected including date(s) and reason(s) for ICU admission, date(s) of ICU discharge, and disposition at time of discharge.

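### SAP 11.8 scores hospital discharge by date alone, so discharge to hospice counts like discharge home, and the date to use after an acute transfer is not stated

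*SAP*

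**What the plan says.** The endpoint list in SAP 3.2 gives only "Discharge from hospital", with no condition on vital status or destination. SAP 11.8 makes it operational: "The number of subjects that were hospitalized and ultimately discharged from the hospital within 30 days from start of treatment will be summarized". An exact interval is computed for each arm, and then "The hospital discharge rate will be compared between the treatments groups using Fishers Exact Test". For timing, the same section says "The date/time subjects were discharged from the hospital will be taken from the Hospitalization eCRF page (dataset: AEHO". The date is the only item it takes from that page.

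Protocol 8.2.8 collects more than the date. For the index stay and any later admission it asks for "date of hospitalization, date of hospital discharge, reason for hospitalization, and disposition at time of discharge". Footnote 19 to the Schedule of Activities (Protocol 1.3, repeated in SAP 17) counts "ICU information, hospitalization, disposition, and mortality" among the outcome data. No efficacy rule in SAP section 11 uses disposition.

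SAP 11.9, on duration of hospitalization, has censoring rules for death in hospital, withdrawal and database lock, and it sums the time over multiple hospitalizations. It has no rule for hospice or for destination.

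**The concern.** A discharge endpoint is read as recovery. In a severely or critically ill population, some discharges may not be recoveries: a dying subject may be moved to hospice, or a subject may be moved to another acute hospital. A rule that uses only a date cannot tell these apart from going home.

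Hospice is the clearer problem. Two subjects with the same prognosis get opposite scores depending on where they die. The one who dies in hospital is not a discharge, and the one sent to hospice shortly beforehand is. In a time-to-discharge analysis the hospice subject also enters as an event, possibly an early one.

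Transfer is a matter of ambiguity. Where there are two consecutive acute stays, 11.8 does not say whether the first or the last discharge date decides the 30-day status. Data are pooled across sites (SAP 9.1), so local transfer practice could enter the endpoint. What is at stake is how one exploratory comparison is interpreted, and whether its scoring is fixed before the blind is broken.

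**Working it through.** **1. The rule applied to four subjects.** The Day 10 timing is assumed for illustration. The plan gives no figure to reproduce on this point: SAP 4 states that no formal sample size calculation was possible, and no discharge rate is assumed anywhere.

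| Subject | Date available to 11.8 | Scored under 11.8 as written |
|---|---|---|
| Goes home, Day 10 | Discharge, Day 10 | Discharged |
| Goes to hospice, Day 10 | Discharge, Day 10 | Discharged |
| Dies in hospital, Day 10 | None, if a death is not entered as a discharge | Not discharged; 11.9 censors the stay at death |
| Transferred to another acute hospital, Day 10 | Day 10, and a later date from the second stay if recorded | Unclear: depends on which date is taken |

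Rows 1 and 2 are identical to the rule. Only the disposition field separates them, and 11.8 does not read it. For row 4, the word *ultimately* in 11.8 points towards the final discharge, but no sentence says so. SAP 11.6 takes dates from the last hospitalization, but that concerns ICU dates and sits beside a listed endpoint of first ICU discharge, so it does not settle the question for the hospital endpoint.

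**2. Size per subject.** Input: about 30 treated subjects per arm (SAP 4).

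- One reclassified subject: 1/30 = 3.3 percentage points on that arm's rate.
- Four in one arm: 4/30 = 13.3 points, for example 24/30 (80.0%) against 20/30 (66.7%).

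**3. Sensitivity of the planned test.** All counts here are assumed. The any-discharge result is taken as either 28/30 against 20/30 or 24/30 against 20/30 (CAP-1002 against placebo). Then k discharges are reclassified as non-events in one arm or in both. Entries are two-sided Fisher exact p-values.

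| k | 28 v 20: CAP-1002 only | 28 v 20: placebo only | 28 v 20: both | 24 v 20: CAP-1002 only | 24 v 20: placebo only | 24 v 20: both |
|---|---|---|---|---|---|---|
| 0 | 0.0211 | 0.0211 | 0.0211 | 0.3817 | 0.3817 | 0.3817 |
| 1 | 0.0575 | 0.0102 | 0.0303 | 0.5675 | 0.2516 | 0.3985 |
| 2 | 0.1253 | 0.0048 | 0.0391 | 0.7787 | 0.1581 | 0.4118 |
| 3 | 0.2326 | 0.0021 | 0.0470 | 1.0000 | 0.0946 | 0.4220 |
| 4 | 0.3817 | 0.0009 | 0.0539 | 1.0000 | 0.0539 | 0.4296 |

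The result moves either way according to the arm in which the reclassified subjects fall. Equal numbers in both arms leave the difference in rates unchanged and move the p-value only a little. In the first scenario, one subject in one arm is enough to move p from 0.0211 to 0.0575.

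**The case against.** The case for leaving the text alone has five parts.

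- **Silence is not a rule.** The SAP never says that hospice or transfer is a success. That is true, and a reader should not infer that the sponsor chose this scoring. But a programmer who follows 11.8 has a date and no exclusion, so a hospice discharge is counted unless someone adds a rule later.
- **Transfers are partly handled.** SAP 11.9 sums multiple hospitalizations and Protocol 8.2.8 records later admissions, so a recorded second stay already lengthens the duration. The wording of 11.8 can also be read as the final discharge. This stands. A reader might infer that every transferred subject becomes an early success, and the documents do not support that. What remains is the unstated choice of date in 11.8.
- **Deaths are not lost.** A death after hospice discharge still enters all-cause mortality (11.1). It also scores 8 on the ordinal scale, which is scheduled through Day 90 and feeds 11.2 and 11.4. This stands and limits the harm to the discharge endpoint itself.
- **Little rests on one p-value.** The endpoint is exploratory, SAP 11 makes p-values descriptive, and SAP 9.3 judges the endpoints together. This lowers the stakes, although a mis-scored endpoint still contributes to that joint judgment.
- **ICU discharge is different.** Protocol 8.2.9 also collects "date(s) of ICU discharge, and disposition at time of discharge", and it is tempting to extend the same definition to 11.6 and 11.7. That would be wrong. A subject stepping down from ICU to a ward is still in an acute hospital, and a rule requiring departure from acute care would remove most of the events the ICU endpoint is meant to count.

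**Conclusion.** The point holds for the hospital-discharge proportion and time to hospital discharge in SAP 11.8. As written, the rule scores a hospice discharge like a discharge home and a death in hospital differently, and it leaves the date open after an acute transfer. The field that would resolve both is collected but unused.

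The impact is modest: about 3.3 points on an arm's rate per reclassified subject at 30 per arm. The documents do not give the number of such subjects, so the p-values shown are illustrations under assumed counts. A reader might infer a bias towards CAP-1002. The documents do not support that: allocation is randomized and blinded, nothing indicates which arm would have more such discharges, and an imbalance could favour either arm. Even four such discharges in one arm and none in the other, giving 24/30 against 20/30, yield p = 0.3817. That would be a misleading 13.3-point difference, not a false positive.

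The conclusion assumes that a hospice discharge produces a discharge date on the Hospitalization page and that a death in hospital is not entered there as a discharge. The case report form is not among the documents, so neither can be checked.

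**What to change.** Before unblinding, amend SAP 11.8 only:

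- Define the event as discharge alive, not to hospice and not to another acute hospital, using the recorded disposition. Use the same event for the 30-day proportion and for time to hospital discharge.
- When a subject is transferred between acute hospitals, take the final discharge of the continuous acute stay.
- State how a hospice discharge is carried in the time-to-discharge analysis, so that it agrees with the proportion.
- Tabulate disposition at hospital discharge by arm.
- Keep the any-discharge analysis as a sensitivity analysis.

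Leave 11.6 and 11.7 out of this definition. The duration analysis in 11.9 already sums multiple hospitalizations and needs no change for this purpose.

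The cost is SAP wording and one table, with no new data if the form is adequate. There are two small downsides. Slightly fewer subjects will count as events. The disposition categories must also be confirmed to separate hospice and acute transfer from other destinations; Protocol 8.2.8 says that disposition is collected but does not list the categories.

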4. SAMPLE SIZE

Up to a total of 60 subjects (approximately 30 in each group, CAP-1002 and placebo) will be enrolled and treated in this study. Subjects who are enrolled and randomized but not treated for whatever reason will be replaced for a total sample size of 60 treated subjects. Adequate information is not currently available for formal sample size calculations for this study. The proposed study size reflects a reasonable estimate of subject numbers to support descriptive and correlative assessments involving clinical safety and efficacy information to support further clinical studies.

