5. RANDOMIZATION, BLINDING, AND REPLACEMENT OF SUBJECTS

Subjects who meet all enrollment criteria will be randomized to receive either CAP-1002 or placebo (1:1 ratio). Only personnel who have been delegated by the Principal Investigator to randomize subjects may complete the task. Subjects will be randomized in the EDC system approximately 1 to 5 days in advance of their first administration. This lead time is to ensure adequate IP shipping time (see IP Manual for shipping specifications). The master randomization list will be generated per the study Randomization Plan and Specifications in

SAS or comparable software and held in confidence by the unblinded programmer preparing the master randomization list.

This is a double-blind, placebo-controlled trial. Investigational product will be prepared for IV infusion by site personnel who have been appropriately delegated by the Principal Investigator. The IP syringes, once prepared, will appear identical for both treatment groups. However, an investigational pharmacist may be able to differentiate CAP-1002 from placebo on the basis of the opacity of the thawed concentrate observed during IP preparation. For this reason, the investigational pharmacists will have limited interaction with the blinded investigative site personnel.

Site personnel and subjects, staff members at clinical research organizations (CROs), and Capricor personnel will remain blinded to treatment assignment throughout trial conduct. An unblinded DSMB, unblinded statistician, and the DSMB administrator will remain firewalled from any blinded individual involved in trial conduct, services, and/or oversight.

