11.3 Time to Clinical Improvement on the Ordinal Scale of Improvement

Time to a clinical improvement (days) will be defined as an improvement in the WHO Ordinal Scale of Clinical Improvement of at least one category (i.e., a 1-point improvement, decrease) from baseline. For example, a 6 at baseline to 5 would constitute an improvement.

Subjects that achieve a clinical improvement will be summarized by number and percentage and analyzed for treatment group differences by use of Barnard's test.

For subjects that did reach a clinical improvement, the time taken to reach a clinical improvement will be analyzed with a Cox PH model with descriptive statistics provided by a Kaplan-Meier analysis, including median time to event, and log-rank test as described above.

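### SAP 11.8 tests 30-day hospital discharge with Fisher's exact test while SAP 11.3 uses the more powerful Barnard's test for the other binary efficacy endpoint, without saying why

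*SAP*

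**What the plan says.** SAP 11.8 (Days in Hospital and Time to Discharge) counts the subjects "ultimately discharged from the hospital within 30 days from start of treatment". It adds an exact interval for each arm ("the two-sided exact 95% confidence intervals will be computed for each treatment's binomial proportion of hospital discharge") and then names the test: "The hospital discharge rate will be compared between the treatments groups using Fishers Exact Test".

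SAP 11.3 (Time to Clinical Improvement) treats its own binary outcome, an improvement of at least one category on the ordinal scale, differently. The proportions are "analyzed for treatment group differences by use of Barnard's test".

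These are the only two efficacy endpoints with a named test of proportions. Both compare the same mITT arms. On arm size, SAP 4 says: "Up to a total of 60 subjects (approximately 30 in each group, CAP-1002 and placebo) will be enrolled and treated in this study". Neither section explains why the tests differ. On power, SAP 4 says: "Adequate information is not currently available for formal sample size calculations for this study".

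**The concern.** The two comparisons have the same structure: an unadjusted 2x2 table, about 30 subjects per arm, 1:1 allocation. The authors chose an unconditional exact test for one and a conditional exact test for the other.

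Fisher's test conditions on the total number discharged, which makes its attainable p-values coarse. In arms this small, its true type I error therefore lies well below the nominal level. Barnard's test also keeps type I error at or below the nominal level, but uses more of it.

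Two things are at stake. The discharge comparison gives up some power. And the two binary p-values, which SAP 9.3 would weigh together as part of the totality of evidence, are not on the same footing, because one is systematically more conservative than the other.

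**Working it through.** **Inputs from the documents.** Two arms of about 30 treated subjects (SAP 4), 1:1 (SAP 5), Fisher's test for discharge (SAP 11.8), Barnard's test for improvement (SAP 11.3).

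**Assumptions.** The documents give no significance level or sidedness for this test; I take two-sided 0.05, to which the two-sided 95% intervals in SAP 11.8 are the only pointer. They give no discharge rates or effect size, so these are varied. SAP 11.3 names no ordering statistic for Barnard's test; I use the pooled Z. There is no power figure in the plan to reproduce.

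**Method.** With 30 per arm there are 31 x 31 = 961 possible tables (x discharged on placebo, y on CAP-1002).

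- Fisher: p is the sum of the hypergeometric probabilities, given x + y, of all tables no more probable than the observed one.
- Barnard: Z = |y/30 − x/30| / √[p̂(1 − p̂)(2/30)], with p̂ = (x + y)/60. The p-value is the maximum over the common rate π of the probability that Z is at least the observed value, on a fine grid of π.
- Power at rates (a, b): the sum of Bin(x; 30, a) × Bin(y; 30, b) over the tables with p ≤ 0.05. Size is the same sum at a = b.

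**One table worked.** Take 20/30 vs 27/30. Then p̂ = 47/60 = 0.783 and Z = 0.2333 / √(0.783 × 0.217 × 2/30) = 0.2333 / 0.1064 = 2.19. Barnard's p is 0.031; Fisher's p is 0.057. Likewise 22 vs 28 gives 0.043 against 0.080, and 15 vs 23 gives 0.035 against 0.060.

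**Rejection regions.** Fisher rejects in 546 tables and Barnard in 590. Barnard's region contains all of Fisher's, plus 590 − 546 = 44 more, so Barnard is never the less powerful test here.

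**Size.** The maximum over the common rate is 2.7% for Fisher and 4.7% for Barnard. At a common rate of 90% the values are 0.9% and 4.1%.

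**Power at 30 per arm**

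| True rates | Fisher | Barnard | Gain (points) |
|---|---|---|---|
| 50% vs 75% | 41.3% | 50.5% | 9.2 |
| 50% vs 80% | 59.6% | 67.8% | 8.1 |
| 60% vs 80% | 29.8% | 36.7% | 6.9 |
| 60% vs 85% | 48.9% | 56.7% | 7.8 |
| 60% vs 90% | 70.5% | 77.9% | 7.4 |
| 70% vs 90% | 37.2% | 48.0% | 10.9 |
| 70% vs 95% | 63.1% | 74.9% | 11.8 |
| *Outside the 7-to-12 range* | | | |
| 60% vs 70% | 7.8% | 11.5% | 3.7 |
| 50% vs 85% | 77.7% | 83.2% | 5.4 |
| 50% vs 90% | 91.4% | 94.1% | 2.7 |
| 40% vs 90% | 98.5% | 99.1% | 0.6 |
| 75% vs 95% | 43.6% | 58.3% | 14.7 |
| 80% vs 95% | 24.1% | 39.2% | 15.1 |

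Gains are taken from unrounded powers. For differences of 20 to 30 points, with placebo discharge from 30% upwards, the gain is about 7 to 12 points, except at 75% vs 95%, where it is larger.

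**Sensitivity to arm size.** Enrolment is only up to 60. At 25 per arm the gain for 20- to 30-point differences runs from about 1 to 11 points.

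**The case against.** The strongest defence is that nothing in SAP 11.8 is wrong. Fisher's test is valid, needs no ordering statistic and no maximisation over a nuisance rate, and is easy to reproduce. A reader might infer from the size figures that the plan mishandles type I error. It does not: a conservative test controls it.

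Second, a reader might infer that the trial loses 7 to 12 points of power outright. The documents do not support that. They give no significance level, discharge rate or effect size, and claim no power. The range belongs to one set of assumptions.

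Third, the consequence is small. SAP 11 says that p-values are descriptive and makes no multiplicity adjustment, so no stated decision turns on this p-value crossing 5%. SAP 11 also makes a risk-adjusted Cox model, Kaplan-Meier curves and a log-rank test the default. The title and second paragraph of 11.8 cover time to discharge, and 11.9 gives censoring rules for hospital stay. The Fisher comparison is therefore not the only analysis of discharge.

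All of this stands, and it limits the weight of the point. It does not explain the inconsistency. SAP 11.3 has the same Cox and log-rank analyses and the same descriptive p-values, and it still names Barnard's test.

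**Conclusion.** The point holds as an unexplained inconsistency with a modest efficiency loss. It is a minor improvement, not an error. At 30 per arm and an assumed two-sided 5% level, Barnard's test dominates Fisher's and keeps its maximum size below 5%. That much does not depend on the discharge rates.

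The size of the gain does depend on them: roughly 7 to 12 points for assumed differences of about 20 to 30 points, and about 0 to 15 points across the wider scenarios at 30 per arm. Even with Barnard's test, power stays below 80% in every 20- to 30-point row of the table, so the change does not make this an adequately powered comparison.

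A reader might also suppose that discharge matters especially because few other endpoints will have enough events. No event rate for any endpoint appears in the documents, so that cannot be said.

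**What to change.** Before unblinding, replace Fisher's exact test with Barnard's test in SAP 11.8, and name the same ordering statistic (for example pooled Z) in both 11.3 and 11.8. If the sponsor prefers to keep Fisher's test, one sentence should say why the two endpoints differ. A matching unconditional confidence interval for the difference in discharge rates is optional; 11.8 now plans intervals for each arm only.

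The cost is one line in each section and slightly more computation, since the test is already planned for 11.3. The one real demand is that the ordering statistic be fixed in advance. A switch made after unblinding could look data-driven, because tables such as 20 vs 27 fall on opposite sides of 5% under the two tests.
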